## Methods

### Design

This study was a single-blinded randomized, placebo-controlled trial. The study was registered on ClinicalTrials.gov (NCT03112473) and conducted in our neurorehabilitation laboratory. Informed consents were obtained before the study began. The study protocol was approved by the ethics committee of the Hong Kong Polytechnic University and conducted in accordance to the Declaration of Helsinki.

As there was no previous study investigating the effect of Bi-TENS+TOT in improving the upper limb motor control in people with stroke, the effect size (Cohen's  $d=0.314$ ) used for the calculation of sample size in this study was obtained from our pilot trial. The sample size was calculated by using G\*power version 3.1.0 (Franz Faul, Universitat Kiet Germany) with  $\alpha$  of 0.05, power of 0.80, correlation among measure of 0.5 and non-sphericity correlation of 1. Ninety-six subjects were necessary to detect a significant between-group difference in the improvement of the upper limb motor control measured by FMA-UE. In accordance to our previous clinical trial, dropout rate of was assumed to be 20%, so a buffer of 24 subjects would be included. A sample size of 120 (30 per group) was used to detect the significant between-group difference finally.

The randomization was conducted by a research assistant who did not involve in the intervention and assessment after the baseline measurement. The eligible subjects were stratified into one of the four groups randomly: Bi-TENS+TOT group, Uni-TENS+TOT group, Placebo-TENS+TOT group and Control group. The stratification was conducted by the online software "Minimize". The factors of age (50-60, 60-70,>70), sex (male, female), type of stroke (ischemia, hemorrhage) and side of lesion (left, right) were balanced in the four groups. To achieve concealment, the allocation information was kept by the research assistant. Following the provision of informed consent, subjects were informed of their allocation to one of four groups, but specific group allocation remained concealed to maintain the blinding of treatment.

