#### **Outcome Measure**

To eliminate the bias, an experienced rehabilitation therapist who was blinded to the group allocation assessed all outcome measures in a random sequence for 5 times, including baseline, mid-intervention (4th week of study), post-intervention (8th week of study), 1-month follow-up and 3-month follow-up.

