### Statistical Analysis

All the quantitative analyses were performed by the SPSS (Version 23.0, IBM, Armonk, NY). Descriptive analysis was used to summarize subjects' demographic information. One-way analysis of variance, Chi-Squared test ( $\chi^2$  test) and Kruskal-Wallis test were used to compare the baseline characteristics of the four groups as appropriate. Intention-to-treat analysis (last observation carry forward) was used. The linear mixed models (LMM) were used to compare the changes over time in variables of interest between those in the Bi-TENS+TOT group and those in the Uni-TENS+TOT group, Placebo-TENS+TOT group and Control group. The maximum likelihood estimation was used to selected the best fit model. The first-order autoregressive structure with heterogeneous variances (AR (1): heterogeneous) was used to estimate the

parameters of statistical model. The intervention effect from pre-intervention to post-intervention was analyzed by LMM. The carryover effect from post-intervention to 3-month follow-up assessment was analyzed using the same LMM method. The significant level was set at 0.05. The post-hoc analysis would be conducted by Bonferroni correction when there was an overall significant difference.

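### The carryover test compares change from week 8 to 3 months, which is zero for a fully lasting benefit as well as for none; no baseline-to-follow-up group difference is named.

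*Combined protocol and SAP*

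**What the plan says.** The Outcome Measure section schedules five assessments: "including baseline, mid-intervention (4th week of study), post-intervention (8th week of study), 1-month follow-up and 3-month follow-up". Baseline and both follow-up scores are therefore available for every outcome.

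The Statistical Analysis section first describes the model in general terms: "The linear mixed models (LMM) were used to compare the changes over time in variables of interest between those in the Bi-TENS+TOT group" and the other three groups. It then names two windows. The first is treatment: "The intervention effect from pre-intervention to post-intervention was analyzed by LMM". The second is follow-up: "The carryover effect from post-intervention to 3-month follow-up assessment was analyzed using the same LMM method".

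Three further rules bear on the second window:

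- Missing data: "Intention-to-treat analysis (last observation carry forward) was used".
- Alpha: "The significant level was set at 0.05".
- Pairwise comparisons: "The post-hoc analysis would be conducted by Bonferroni correction when there was an overall significant difference".

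The plan names no group difference in change from baseline to either follow-up visit and no group difference at 3 months. It gives no margin or confidence-interval criterion for retention and does not say how a null carryover result will be read.

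**The concern.** Follow-up visits are there to show whether a treatment benefit lasts. A comparison of change that restarts at week 8 answers a narrower question: whether the groups converge or diverge once treatment stops. A fully lasting benefit, the best outcome for the experimental arm, gives the same expected value as no benefit.

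Retention would then have to be argued from a non-significant change, and non-significance is not evidence of no loss. Pairwise comparisons follow only an overall significant difference, so under full retention the follow-up window would usually give no Bi-versus-Uni, Bi-versus-Placebo or Bi-versus-Control comparison. Carrying week-8 scores forward builds some apparent retention into the data.

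Any statement about lasting benefit is at stake. The pre-to-post analysis is not affected.

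**Working it through.** **Inputs.** From the Design section: d = 0.314, correlation 0.5, power 0.80, 96 subjects, 20% dropout, 120 subjects (30 per group). From Statistical Analysis: alpha 0.05, taken here as two-sided for pairwise tests. Assumed: correlations of 0.8 and 0.9, effects in SD units, the pattern of arm effects, and the timing of dropout. The Design section does not say that 0.314 is a gap between two arms; it is used below as an illustration.

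**1. The plan's own figure.** For a group-by-time interaction, λ = f²·N·m/(1−ρ), df1 = (k−1)(m−1), df2 = (N−k)(m−1). With f = d/2 = 0.157, k = 4, m = 3, ρ = 0.5 and N = 96, λ = 0.157²·96·3/0.5 = 14.20, df = 6 and 184, and power is 0.803. So 96 reproduces, and 96/0.8 = 120. The values m = 3 and f = d/2 are inferred. With f = 0.157, two, four or five visits give 116, 84 or 76. Three visits match either named window (baseline, week 4, week 8; or week 8, 1 month, 3 months) and not a five-visit model.

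**2. What the carryover contrast measures.** Let D(t) be the between-group difference at time t, with D(baseline) = 0.

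| Truth | Pre to post | Post to 3 months | Baseline to 3 months |
|---|---|---|---|
| Bi gains 6, Uni gains 3, both keep it | 3 | (6−6)−(3−3) = 0 | 3 |
| Neither gains | 0 | 0 | 0 |
| Bi gains 6, Uni gains 3, difference fully lost | 3 | −3 | 0 |

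Only the last column is the benefit remaining. In simulation (30 per arm, one arm better by an assumed 0.8 SD), the overall four-arm test of post-to-3-month change rejects 5.2–5.5% of the time under full retention and 4.7–4.9% under no benefit. Under complete loss it rejects 89–97%. The baseline-to-3-month test rejects 83–90% under full retention and 4.5–5% under no benefit.

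**3. What a null carryover result leaves open.** For one pair of arms, the SD of change is σ√(2(1−ρ)). Power to detect complete loss of 0.314 SD (noncentral t, 58 df), and the 95% interval half-width t(0.975, 58)·√(2(1−ρ))·√(2/30):

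| ρ | Power, alpha 0.05 | Power, alpha 0.0167 | Half-width (SD) |
|---|---|---|---|
| 0.5 | 0.223 | 0.114 | 0.517 |
| 0.8 | 0.473 | 0.302 | 0.327 |
| 0.9 | 0.762 | 0.602 | 0.231 |

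The 0.0167 column assumes three Bonferroni comparisons; the plan does not state the number. With an observed change of zero, the interval still contains a 0.314 SD loss at ρ = 0.5 or 0.8 and excludes it at 0.9.

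For the overall four-arm F test at ρ = 0.5 under complete loss, power is 0.872 if week-8 effects are 0.9, 0.6, 0.3 and 0 SD, and 0.204 if they are 0.314, 0, 0 and 0 SD. A three-visit simulation gives 0.78–0.91 and 0.16–0.20, depending on when the loss occurs.

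**4. Carry-forward.** Anyone last seen at week 8 or earlier gets a post-to-3-month change of exactly zero. If a fraction p of each arm has no later visit, a true loss of 0.314 SD has expected value (1−p)·0.314:

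| p | Expected loss (SD) | Simulated pairwise power, ρ = 0.5 | Simulated pairwise power, ρ = 0.9 |
|---|---|---|---|
| 0.1 | 0.283 | 0.205 | 0.711 |
| 0.2 | 0.251 | 0.184 | 0.651 |

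The Design section allows for dropout ("dropout rate of was assumed to be 20%, so a buffer of 24 subjects would be included") but does not say when it occurs, so p = 0.2 is the case where all of it leaves no visit after week 8.

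**The case against.** The strongest objection is that the plan lists no fixed effects and never writes the carryover contrast out. A mixed model on week 8, 1 month and 3 months would normally also give a group main effect, and that is not zero for a lasting benefit. With one arm better by 0.5 SD at all three visits, 30 per arm and correlation 0.5, it rejects about 66% of the time; at 0.8 SD, about 98%. This is correct, but a main effect is not a comparison of change over time, which is how the plan describes its models, and the plan does not name it as the carryover test.

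Second, the two windows together do separate lasting benefit from no benefit, because the pre-to-post contrast is 3 in one case and 0 in the other. That stands. What remains is that retention would rest on a non-significant change, with no margin or interval to judge it by.

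Third, change after treatment is a legitimate question, and the plan does not say that a null result proves retention. Nor does it rule out confidence intervals. Both points are fair: the plan is silent on how the result is to be read or reported, and that silence needs filling.

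Fourth, the power figures run from 18% to 87% across assumptions, use simpler models than the planned heterogeneous AR(1), and treat 0.314 as a pairwise gap without support in the Design section. They show that a null result can be uninformative; they do not show that it will be. Carry-forward also affects a baseline-to-follow-up contrast, so the remedy has to deal with it there too.

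**Conclusion.** The concern holds. On the natural reading of the text, the carryover test is a between-group difference in change from week 8 to 3 months. Its expected value is zero for a fully lasting benefit and for no benefit, and no direct estimate of the remaining benefit is named, although the visits needed for one are collected. That conclusion needs no numerical assumption beyond this reading of the contrast.

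How often a complete loss would be missed does depend on assumptions. For a 0.314 SD pairwise loss with 30 per arm and alpha 0.05, the chance of missing it is 78% at correlation 0.5 (1 − 0.22), 53% at 0.8 and 24% at 0.9. With well-separated arms the overall test misses it only 13% of the time (1 − 0.87). Carry-forward moves the contrast toward apparent retention by the fraction of subjects with no visit after week 8. This should be corrected before any claim of lasting benefit is made.

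**What to change.** 1. Name as the test of lasting benefit the between-group difference in change from baseline to 1 month and from baseline to 3 months, for Bi-TENS+TOT against each of the other three groups. Report 95% confidence intervals, from a mixed model that includes baseline and the follow-up visits.
2. Keep the post-to-follow-up change, with its interval, as a description of loss or late gain. State that its non-significance is not evidence of retention.
3. Report, per arm, how many follow-up values are carried forward, and repeat the contrasts on observed values only. A carried-forward week-8 score counts as retained benefit in the baseline-to-follow-up contrast as well.

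The cost is a few more contrasts from data already collected. The Subjects section reports 120 subjects already recruited, so the contrasts should be labelled post hoc if data have been analysed. The change does not raise pairwise power: at 0.314 SD and correlation 0.5, the overall baseline-to-3-month test rejects only 20% of the time when one arm alone differs and keeps its benefit. What it provides is a direct estimate of the remaining benefit with its uncertainty.

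### The three named Bi-TENS+TOT comparisons appear to sit behind an overall test and a Bonferroni correction; direct Holm tests meet the same 5% error limit and are never less powerful

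*Combined protocol and SAP*

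**What the plan says.** The Statistical Analysis section uses linear mixed models (LMM) to compare changes over time "between those in the Bi-TENS+TOT group and those in the Uni-TENS+TOT group, Placebo-TENS+TOT group and Control group". That is three comparisons out of the six possible pairs. The section continues: "The significant level was set at 0.05", and "The post-hoc analysis would be conducted by Bonferroni correction when there was an overall significant difference". It does not say which overall term is tested, how many pairs the correction covers, or whether the three LMM comparisons count as post-hoc.

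The Design section gives the sample size: "Ninety-six subjects were necessary to detect a significant between-group difference in the improvement of the upper limb motor control measured by FMA-UE". The inputs are a pilot effect of d = 0.314 and alpha "of 0.05, power of 0.80, correlation among measure of 0.5 and non-sphericity correlation of 1". After a 20% dropout allowance the plan states: "A sample size of 120 (30 per group) was used to detect the significant between-group difference finally". No power is given for any pairwise comparison. The analysis is by intention to treat with the last observation carried forward, so all 30 per arm are analysed.

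**The concern.** The plan knows in advance which three comparisons it wants, yet treats them as follow-up to a four-arm test. That test asks a different question. Under Intervention, the Control arm receives no active treatment, so the overall test can be significant because Control alone differs, with no added effect of TENS. It can also miss, and then block a named comparison that would have passed on its own.

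Bonferroni is then applied, although a step-down version with the same guarantee is available. If the correction runs over all six pairs, half of the alpha goes to pairs that the plan does not name. At stake is power for the comparisons that carry the trial's claim, in arms of 30.

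**Working it through.** **1. Reproduce the planned size.** Treat 96 as the size for a repeated-measures group-by-time interaction: 4 groups, 3 visits (baseline, week 4, week 8), f = d/2 = 0.157, correlation 0.5, sphericity 1.

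- Noncentrality: f² × N × 3/(1 − 0.5) = 0.157² × 96 × 3/0.5 = 14.2.
- Degrees of freedom: 6 and 2 × (96 − 4) = 184. Power is 0.803, so N = 96 is reproduced.
- 96/(1 − 0.20) = 120, or 30 per arm.

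The 80% is therefore power for an overall test, not for any pair.

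**2. Compare the rules.** With three contrasts, the gated rule rejects a pair only if the overall p is below 0.05 and the pair's p is at most 0.05/3 = 0.0167. Holm compares the ordered p-values with 0.0167, 0.025 and 0.05. Every p-value at or below 0.0167 passes its Holm step, so each gated Bonferroni rejection is also a Holm rejection. Both rules hold family-wise error at 5% or below whichever effects are real. No simulation is needed for this.

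**3. Size the loss.** The documents give no effect pattern, so several were assumed, each scaled to f = 0.157 with a linear gain over visits. The SD of change is √(2 × (1 − 0.5)) = 1 SD.

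- Only Bi differs, by g: 24 × 0.375g²/0.5 = 18g² = 14.2, so g = 0.89 SD.
- Graded in equal steps a (Bi, Uni, Placebo, Control): 24 × 2.5a²/0.5 = 120a² = 14.2, so a = 0.34 SD.

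Closed-form check for the first pattern at 30 per arm: standard error √(2/30) = 0.258 and 0.888/0.258 = 3.44. Against critical values of 2.41 (three pairs) and 2.66 (six pairs), ungated Bonferroni has power 0.85 and 0.78.

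Simulation at 30 per arm: 100,000 trials per pattern, two-sided tests on baseline-to-week-8 change with the pooled error term. The gate is either a 3-df test of change or the 6-df group-by-time test. Entries are % rejected; B3 and B6 are Bonferroni over three and six pairs.

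| Pattern, comparison (difference in SD) | Holm, no gate | B3, no gate | B3, 3-df gate | B3, 6-df gate | B6, 3-df gate | B6, 6-df gate |
|---|---|---|---|---|---|---|
| Only Bi differs, each (0.89) | 90.3 | 84.7 | 84.0 | 81.1 | 78.0 | 76.2 |
| Graded, Bi–Uni (0.34) | 24.9 | 14.3 | 14.3 | 14.1 | 9.5 | 9.5 |
| Graded, Bi–Placebo (0.69) | 66.3 | 60.1 | 59.9 | 58.8 | 50.4 | 49.9 |
| Graded, Bi–Control (1.03) | 94.7 | 94.2 | 92.7 | 88.3 | 90.4 | 86.7 |
| Uni and Placebo at half effect, Bi–Uni (0.54) | 49.0 | 38.2 | 38.1 | 37.7 | 29.1 | 28.9 |
| Same, Bi–Control (1.09) | 96.6 | 96.4 | 94.3 | 89.3 | 93.2 | 88.7 |
| Bi = Uni, both above the rest, Bi–Placebo (0.77) | 74.5 | 71.4 | 71.0 | 69.3 | 62.3 | 61.4 |
| Only Control differs, Bi–Control (0.89) | 84.8 | 84.7 | 84.0 | 81.0 | 77.9 | 76.0 |
| No effect, any false rejection | 4.5 | 4.5 | 2.9 | 1.7 | 2.0 | 1.2 |

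Against Holm, gated B3 loses from 84.8 − 84.0 = 0.8 to 49.0 − 37.7 = 11.3 points. Gated B6 loses from 96.6 − 93.2 = 3.4 to 49.0 − 28.9 = 20.1 points.

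**4. Attribute the loss.** For graded Bi–Uni, replacing Holm by B3 costs 24.9 − 14.3 = 10.6 points and the 6-df gate a further 0.2. At half effect the two parts are 10.8 and 0.5. If only Bi differs, the 6-df gate does take a visible share: 5.6 points from B3, then 3.6 from the gate. For graded Bi–Control the order reverses: 0.5 from B3, then 5.9 from the 6-df gate. The chance of at least one finding is the same for Holm and ungated B3, because their first step is identical, so with B3 any loss there is due to the gate. In the graded pattern it falls from 95.4% to 93.7% (3-df gate) or 88.9% (6-df gate).

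**The case against.** The strongest reply is that the planned rule is valid. It keeps family-wise error below 5%, and under no effect its actual error is lower than Holm's: about 2 to 3% with three pairs, against about 4.5%. That stands. Preferring Holm is a point of efficiency, and the accurate statement is that the gate gives no needed protection against the plan's own 5% limit.

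Second, the text is ambiguous. If the three contrasts are read directly from the LMM and only further pairs are post-hoc, the gate does not touch them. That also stands, and it limits confidence in the size. It does not remove the gain under any reading that uses a gate or Bonferroni, and it is itself a reason to fix the wording.

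Third, a reader might infer that the gate roughly halves power for bilateral against unilateral TENS. The figures do not support that. In the graded pattern power does fall from about 25% to 14%, but almost all of this is Bonferroni instead of Holm, and a drop that large is particular to that pattern. Nor does Holm rescue the comparison there: 25% power is still low.

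**Conclusion.** The point holds as a cheap improvement. On the natural reading, the rule for the three named comparisons is never more powerful than direct Holm tests at the same 5% limit, and it is underspecified. At the analysed 30 per arm the loss is about 1 to 12 points per truly different comparison with three pairs (about 6 to 9 if only Bi-TENS+TOT differs) and about 3 to 20 with six. For Bi against Uni, nearly all of it comes from Bonferroni when effects fall off across the arms. A 6-df gate mainly lowers Bi against Control and the chance of any finding.

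These sizes rest on assumed effect patterns, a linear gain, compound symmetry in place of the planned heterogeneous AR(1), two-sided tests, no missing data, and a gate of 3 or 6 df. A reader might want a single figure for the loss, or one based on 24 per arm. The documents support neither: they fix no effect pattern, gate or number of pairs, and carrying the last observation forward keeps all 30 in the analysis.

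**What to change.** Pre-specify three contrasts from the LMM on FMA-UE change from baseline to week 8: Bi-TENS+TOT minus Uni-TENS+TOT, minus Placebo-TENS+TOT and minus Control. Test them by Holm at family-wise 0.05 without an overall gate. Report the overall group-by-time test as descriptive and the other three pairs as exploratory.

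The cost is a few lines of text and three contrast statements, with no extra participants or visits. One small drawback is that Holm has no simple matching simultaneous intervals, so Bonferroni intervals should be shown alongside. Because the Subjects section already describes a recruited sample, the change should be dated and made before outcomes are compared by arm; otherwise the Holm results should be labelled supplementary.
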